2.1 Rationale for Target Population

The aim of this clinical trial is to evaluate whether or not treatment with IL-1Ra improves clinical outcome following aSAH. This research builds on our recent phase II study of IL-1Ra in aSAH that has shown significant reductions in plasma inflammatory markers in the treatment compared with control. It will provide definitive evidence of the efficacy or otherwise of this treatment.

Patients with aSAH even after acute management and securing of the aneurysm to prevent rebleeding, have significant mortality and morbidity with 25% dead or disabled at one year²⁹. They may have symptoms associated with early brain injury which may include acute neurological deterioration, often occurring between 3 and 21 days following ictus and affecting mainly those with poor grade SAH. A higher proportion of patients experience problems such as fatigue, memory and concentration difficulties that contribute significantly to their difficulties returning to work and normal family life⁹. In a post -hoc analysis of the STASH trial, CRP at baseline was associated with clinical outcome in 'good grade' (WFNS 1&2) patients¹⁵.

Our trial is needed now because pharmacological attempts to improve outcome to date have been disappointing, with only nimodipine, a selective calcium channel blocker, shown to improve outcome in the acute management of aSAH³⁰. Prevention of cerebral ischaemia remains a key target⁹. Reducing the impact of cerebral ischaemia following aSAH would make a very significant societal and economic impact⁵.

2.1.1 Justification of IMP dose and treatment duration

Patients will be randomised to receive study drug or placebo for a maximum 21 days from ictus. The length of treatment reflects the time course for risk of vasospasm that is generally accepted through the neurosurgical community³¹. Moreover, there is evidence that breakdown products of extravasated blood that are associated with IL-1 mediated inflammation are present in the cerebrospinal fluid for three weeks in 70% of patients following SAH³².

The dose of SC IL-1Ra has been chosen following extensive pharmacological research. The peak plasma concentration achieved by injection of 100 mg of SC Kineret® is achieved within a maximum of 7 hours. This results in a significant variation (peak-trough) in plasma concentration when a once daily dose is administered. While this may not be an issue for treatment of chronic inflammatory diseases such as rheumatoid arthritis, it was our objective to achieve steady plasma concentrations when antagonising the acute inflammatory response following aSAH.

Using PK and safety data from Amgen, with whom we have collaborated for a number of years before the patent transfer to SOBI, we modelled different dosing regimens of the drug. A twice daily injection of 100 mg of Kineret® was predicted to achieve steady concentrations of the drug (Fig 3). This dose was subsequently used in a phase II study funded by the MRC (EudraCT 2011-001855-35). We have since published the results that demonstrated that the plasma concentrations achieved using this regime were within our predicted intervals and that the administration was feasible³³. During our proposed study, we will be using this same dose and duration of drug that was shown to be effective in reducing inflammation in our patient cohort.

[figure not shown]

Figure 3: PK profiles of Kineret® in plasma following o.d. (real) and b.d. (simulated) SC administration

2.1.2 Justification for inclusion prior to confirmation of aneurysm

The initial clinical and computed tomography (CT) scan diagnosis on arrival in the neurosurgical centre is normally of SAH (not aSAH) because a proportion (around 20%) of patients with confirmed SAH is subsequently found on angiography not to have aneurysm. These non-aneurysmal SAH (non-aSAH) patients usually have mesencephalic bleed which has a much better outcome than aneurysmal bleed. Diagnosis of aneurysm requires an angiogram (usually CT angiogram; CTA) which may not be performed immediately.

Earlier treatment is known to be associated with better outcome in preclinical studies^{34,35} so to avoid delay, we propose to randomise following the diagnosis of SAH which may be prior to confirmation of aneurysm. People subsequently found to be non-aneurysmal (usually angiogram is performed within 48 hours or less of arrival at the neurosurgical centre) will be withdrawn from the trial. We will encourage early approach to allow people as much time as they need to consider participation and so approaching as soon as the initial SAH diagnosis is made seems most logical. Patients for whom aneurysm is not confirmed will not be included in outcome analysis although they will be included in Adverse Event monitoring.

2.2 Assessment and Management of Risk

aSAH is a common cause of stroke related death and disability affecting younger people than the more common ischaemic stroke. Clinical outcome remains relatively poor and even those who survive the initial bleed rarely feel back to normal when they return home. Many survivors report ongoing symptoms e.g. fatigue, attention and memory deficits for months or years following ictus and return to work is often problematic. aSAH in 2005 was estimated to cost £205 million annually in the NHS including hospital care costs and care after discharge. Community health and social service care costs were estimated to be around 18% of the total cost⁵. Any treatment that improves modified Rankin score (mRS) could reduce length of hospital stay and will reduce the patient's dependence on formal and informal carers following discharge. It would be cost effective.

IL-1Ra has been evaluated in several clinical trials and is well tolerated with a consistent safety profile. Clinically significant adverse events in our stroke and aSAH studies were no more common with IL-1Ra than with placebo. There is evidence of an increased frequency of serious infections in people treated with IL-1Ra long term, for example in conditions such as rheumatoid arthritis, but we have now treated patients with both ischaemic stroke and aSAH with IL-1Ra without safety concerns. We have found no difference in infection rates between treated and non-treated/placebo patient groups even though patients with aSAH are at risk of infection, as they may require intensive or high dependency care and be at risk of pneumonia. Indeed we have evidence that IL-1Ra appears in vitro to reverse the immune suppression associated with ischaemic stroke²⁸.

IL-1Ra is contraindicated in people who are already taking Tumour Necrosis Factor-alpha (TNF- α inhibitors) so a medication history will be taken prior to inclusion.

The drug Summary of Product Characteristics (SmPC) states that IL-1Ra should not be administered in renal failure (Creatinine clearance < 30ml/min) or in neutropenia (absolute neutrophil count (ANC) < 1.5×10^9 L). Blood will be taken and results medically reviewed prior to inclusion in the trial. Injection site reactions may occur with IL-1Ra administered SC but we have found that by administering the injections in different anatomical sites each time these are generally well tolerated; just two patients (n=68 receiving IL-1Ra) withdrew from our phase II study because of injection site reactions. All adverse events will be reported.

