7.8 Withdrawal Criteria

Participants without confirmation of aneurysm within 72 hours of randomisation and those patients found to be non-aneurysmal post randomisation will be withdrawn from treatment. If participants are withdrawn for this reason they will continue to be followed up until their safety (30 days post randomisation) assessment. While baseline plasma samples collected from these participants will not be analysed for this trial, the samples will be shipped to the trial centre (see section 7.9) for potential use in future research (provided consent was given for this). If consent was not given for use of samples in future research, the sample must be destroyed at the participating site as per local procedure

In the event of death between randomisation and the diagnosis of aneurysm (usually by CTA), these participants will be excluded as 'Failed To Confirmed Aneurysm' and this event should be reported as detailed in notification of death (section 9.5).

Participants have the right to withdraw from the trial treatment or trial participation at any time, without having to give a reason and without any effects on their clinical care. The withdrawal process will be explained prior to consent.

If a participant is withdrawn from trial treatment, study drug will be stopped immediately and no further blood samples will be obtained. Subsequent assessments of patient safety and an end of study outcome will be completed as planned. All data and samples will be retained and included in analyses. Trial treatment should be stopped for the circumstances listed below.

- Uncontrolled AE/SAE that is related to, or potentially related to, study drug;
- Participant or personal legal representative decision, or at the PI discretion;
- If a severe allergic reaction occurs administration of IL-1Ra should be discontinued and appropriate treatment initiated;
- If participants become neutropenic (ANC <1.5 x 10⁹/l), IL-1Ra treatment should be discontinued;
- Pregnancy;
- Symptomatic deterioration where the investigator feels the participant's receipt of study drug is no longer clinically appropriate;
- Study suspended or stopped for any reason.

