Subarachnoid haemorrhage patients may suffer uncontrolled AEs or SAEs due to the nature of the condition. Therefore only uncontrolled AEs or SAEs that are related to, or potentially related to, study drug should be a direct reason for withdrawal from trial treatment. If a participant suffers any uncontrolled AE or SAE that is not related to study drug, but that in the investigator's opinion it would be in the participant's best interest to end trial treatment, the participant can be withdrawn from trial treatment based on the penultimate point listed above.

If the participant withdraws from trial participation, no further assessments will be performed. The information required for the final 30 day safety information will be gathered from secondary sources including clinical records. Study data and samples will be retained and included in analyses unless the participant requests it be destroyed. It is the responsibility of the participating site research teams to ensure the participant's wishes are met. Samples stored at the participating site must be destroyed as per local procedure and the central laboratory and Manchester CTU must be notified of the participant's request for their data and samples to be destroyed.

Participants and their representatives do not have to give a reason for their withdrawal. However, where available, the research team will record reason for withdrawal or lack of this in the medical notes and the CRF.

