8.1.4 Concomitant medication

Concomitant medications may be given as medically indicated. Concomitant medications will be checked at screening, through daily liaison between the site PI or delegate and the direct clinical care team and at the pre-specified adverse event (AE) reporting checks at the day 3-5 assessment, between day 10-12 and on the final day of study treatment. Treatment with TNF- α inhibitors (e.g. etanercept or other TNF antagonists) is not permitted during the period of the study intervention and for 48 hours following its discontinuation. Live vaccines should not be given concurrently with study drug. Therefore if a participant is required to take any of the above medications as part of clinical care they would be withdrawn from study treatment (see section 7.8).

Any other medications that are known or subsequently reported as having, or potentially having, interactions with study drug and are not recommended to be used concurrently with study drug will be restricted from this time period. If the medication is part of clinical care the participant will be withdrawn from study treatment (section 7.8).

Patients who are currently in receipt of IL-1Ra will not be eligible to participate for patient safety reasons.

The formation of CYP450 enzymes is suppressed by increased levels of cytokines (e.g., IL-1) during chronic inflammation. Thus, it may be expected that for an IL-1 receptor antagonist, such as Kineret, the formation of CYP450 enzymes could be normalized during treatment. This would be clinically relevant for CYP450 substrates with a narrow therapeutic index (e.g. warfarin and phenytoin). Upon start or end of Kineret treatment in patients on these types of medicinal products, it may be relevant to consider therapeutic

Protocol V7.0; 20 Sep 2019

monitoring of the effect or concentration of these products and the individual dose of the medicinal product may need to be adjusted.

All standard care and medications will continue unaffected by study participation.

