8.1.5 Special warning and precautions for use

Please see current approved version of the SmPC for full details of these events below.

Allergic reactions:

Allergic reactions, including anaphylactic reactions and angioedema have been reported uncommonly. The majority of these reactions were maculopapular or urticarial rashes.

If a severe allergic reaction occurs, administration of study drug should be discontinued and appropriate treatment initiated.

Hepatic events:

Investigators should exercise caution when administering study drug to patients with a history of severe hepatic impairment or liver dysfunction, defined as total bilirubin above the ULN (excluding patients with Gilbert's syndrome), AST or ALT >3 times the ULN or alkaline phosphatase >2.5 times the ULN.

Renal impairment:

Study drug should be used with caution in patients with moderate renal impairment (creatinine clearance or eGFR 30 to 59 ml/minute).

Serious infections:

Investigators should exercise caution when administering study drug to patients with a history of recurring infections or with underlying condition which may predispose them to infections (e.g. Asthma).

When diagnosing infection in a patient in the study, investigators should not rely solely on the CRP level as reduction in plasma CRP has been seen in patients receiving IL-1Ra. However, the reduction is modest and therefore unlikely to impact on clinical decision making.

Consideration should be given to the higher risk of infection in all grades of aSAH patients compared to the normal population (e.g. the RA patient referenced in the SmPC). It is important to note that there is no evidence in the SmPC or from our previous trials (see section 0 for more detail) to support withdrawal of study drug in the event of a serious infection in this population. The decision to interruption or stop IL-1Ra is at the discretion of the local investigator.

Neutropenia:

Events of neutropenia have been observed in previously RA studies when administered long-term. Therefore precaution is recommended in patient with a history of neutropenia.

If a participant becomes neutropenic (ANC < $1.5 \times 10_9$ /I) the ANC should be monitored closely and study drug should be discontinued.

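### Protocol section 2.2 reports that IL-1Ra should not be given at creatinine clearance below 30 ml/min, but no on-treatment stop is written for renal function falling below that value

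*Protocol*

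**What the plan says.** Section 2.2 of the protocol names three states in which the drug should not be used. On the label it says that it "states that IL-1Ra should not be administered in renal failure (Creatinine clearance < 30ml/min) or in neutropenia", with neutropenia set at an ANC below 1.5 x 10^9/L. On medication it says that "IL-1Ra is contraindicated in people who are already taking Tumour Necrosis Factor-alpha" inhibitors. The controls that section 2.2 itself describes, a medication history and a medical review of bloods, both take place before inclusion.

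For the treatment period the relevant text is as follows.

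- **Neutropenia.** The stop list in section 7.8 has an item beginning "If participants become neutropenic", with the ANC threshold. Section 8.1.5 repeats it: "the ANC should be monitored closely and study drug should be discontinued".
- **TNF-alpha inhibitors.** Section 8.1.4 bars them during treatment and says that "if a participant is required to take any of the above medications as part of clinical care they would be withdrawn from study treatment".
- **Renal function.** Section 8.1.5 says "Study drug should be used with caution in patients with moderate renal impairment", defined as 30 to 59 ml/minute. It says nothing about values below 30, and the section 7.8 list has no renal item.

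**The concern.** Section 2.2 puts clearance below 30 ml/min and neutropenia in one sentence with equal standing. During treatment they part company. For renal function, the protocol guides the investigator in the moderate range and falls silent in the worse range, where it has said the drug should not be given.

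A site that follows the stop rules in sections 7.8 and 8.1.5 as written could therefore continue 100 mg twice daily, up to day 21 from ictus, in a participant whose clearance has dropped below 30 ml/min. The event is foreseeable: Table 4 lists renal failure among the events of the normal SAH disease process and rates it common. What is at stake is participant safety. The point concerns renal decline after treatment starts, not the entry criterion.

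**Working it through.** No calculation applies, so the check sets the provisions side by side.

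| State barred in section 2.2 | Entry control | Written stop on treatment |
|---|---|---|
| TNF-alpha inhibitor use | Exclusion 9 (6.2) | Yes: 8.1.4, referring to 7.8 |
| ANC < 1.5 x 10^9/L | Exclusion 5 (6.2); pre-randomisation check (7.7.1) | Yes: 7.8 and 8.1.5 |
| Creatinine clearance < 30 ml/min | Exclusion 6 (6.2, clearance or eGFR); pre-randomisation check (7.7.1) | None |

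Count: 3 states, 2 with a written on-treatment stop, 3 - 2 = 1 without.

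The next question is whether a general stopping route fills the gap.

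1. **Drug-related events.** Section 7.8 lists "Uncontrolled AE/SAE that is related to, or potentially related to, study drug". The text below the list says that only such related events should be a direct reason for withdrawal. Because Table 4 places renal failure among disease-related events, a renal decline that the investigator attributes to the haemorrhage would not meet this item.
2. **Unrelated events.** For these, section 7.8 says that "the participant can be withdrawn from trial treatment based on the penultimate point listed above". That point is symptomatic deterioration. A fall in clearance seen only on a blood result need not be symptomatic.
3. **Discretion and best interest.** Investigator discretion (7.8) and section 9.4 permit stopping. Neither requires it and neither mentions a renal value. Section 8.1.3 leans the other way by asking sites to avoid interrupting study drug.
4. **Label pointer.** Section 8.1.5 opens with a general referral to the current SmPC. The neutropenia paragraph sits under the same referral and still carries its own explicit stop.

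The last question is whether there is an occasion on which a renal threshold could be applied. Table 1 schedules a research-staff review of clinical bloods at days 3-5 and 10-12, on the final treatment day and at day 30. Section 7.7.1 says that later renal tests, done at the clinical team's discretion, will be looked at in those reviews. Section 7.7.2 adds daily liaison with the clinical team. The occasions exist, and the neutrophil count has a threshold to be read against. The renal result has none.

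**The case against.** The strongest reply is that the bar is already written, with a value, in section 2.2. It is worded as a bar on administration and not only on entry, and section 8.1.5 sends investigators to the SmPC. On that reading a missing item in section 7.8 is a matter of clarity; the TNF-alpha rule is not in that list either. Participants are inpatients under daily review, several general routes allow stopping, and section 8.1.3 already lets the investigator restart after an interruption. The SmPC itself is not reproduced, so whether it asks for discontinuation or withholding when renal function falls during a short course cannot be told from the protocol. No number of affected participants is given, and the new rule would act only on results that clinicians had already obtained.

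Part of this stands. A clinician may well stop the drug without a written rule, the frequency is unknown, and the choice between stopping and withholding belongs to the sponsor's clinicians. It does not remove the point. The only controls that section 2.2 attaches to its statement are pre-inclusion checks. The TNF-alpha rule, although outside the section 7.8 list, is an explicit instruction to withdraw treatment, and the renal state has no such instruction anywhere. Where the protocol wants case-by-case judgement it says so with reasons, as it does for serious infection in section 8.1.5; no such choice is recorded for renal function.

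**Conclusion.** The concern holds. Of the three states that section 2.2 treats as barring the drug, clearance below 30 ml/min is the one without a stop during treatment. The conclusion rests on the protocol text alone and on taking section 2.2's report of the label at face value.

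The number of participants affected cannot be derived. Table 4's common category runs from 1/100 to below 1/10 for renal failure, but it does not define renal failure as clearance below 30 ml/min, so it shows only that the event is expected. The gap is one of safety conduct and belongs in the protocol, not in an analysis plan. The sample size and the primary comparison are not in question. It should be corrected, since the change is small and makes the protocol's stop rules agree with its own risk assessment.

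**What to change.** Add one sentence to the section 7.8 list and one to the renal paragraph of section 8.1.5: *if creatinine clearance or eGFR is found to be below 30 ml/minute during treatment, study drug should be discontinued*. If the sponsor's clinicians prefer, *withheld* can replace *discontinued*, with a stated condition for restarting. At the day 3-5 and day 10-12 blood reviews in Table 1, compare the latest available renal result with this threshold and record the check in the CRF. Use the daily liaison in section 7.7.2 to pick up results that arrive between reviews.

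The cost is two sentences in an amendment and one CRF check, with no additional blood draws. A few more participants may discontinue; they would still be followed and, if aSAH is confirmed, analysed as allocated (section 11.7). Under section 7.8, anyone withdrawn from treatment before the day 3-5 research sample would not have that sample taken, a small possible loss to the IL-6 analysis. The rule cannot act on a decline that nobody has measured, because renal testing after entry remains at the clinical team's discretion.

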3. OBJECTIVES AND OUTCOME MEASURES/ENDPOINTS

3.1 Aim

• To determine whether there is clinical efficacy of treatment with IL-1Ra following aSAH;

3.2 Primary Objective

Our primary objective is to answer the specific question:

 Does 100 mg twice daily SC injection of IL-1Ra commenced within 72 hours of ictus and administered for a maximum of 21 days from ictus in patients with aSAH improve their clinical outcome as assessed by the modified Rankin Scale at 6 months?

3.3 Secondary Objectives

- Does this treatment improve patient-reported outcomes such as mood, fatigue and quality of life?
- Is any effect of this treatment on clinical outcome correlated with its effect on plasma IL-6 concentration?

